6 PARTICIPANT DISPOSITION

A flowchart will be produced showing the flow of participants throughout the study. The numbers of participants;

- Randomised from the relevant centres
- Having each pre-operative and post-operative delirium assessment
Surgical duration
- Having each pre-operative and post-operative MMSE assessment
Surgical duration
- Lost to follow-up
- Dying during the 1 year follow-up will be summarised.

7 EFFICACY ANALYSES

7.1 Primary endpoint analyses

The primary endpoint analysis will compare the primary endpoint, diagnosis of delirium at any post-operative assessment, in the intention-to-treat population, using a Mantel-Haenszel Chi-square test, stratified by study-centre groups. The pooled estimate of the odds ratio and 95% confidence interval from this analysis will be used to summarise the statistical comparison. Analyses will be undertaken on both the Intention-to-Treat population and the Per-Protocol populations.

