4 GENERAL ANALYSIS DEFINITIONS

4.1 Treatment Allocation

Participants are randomised in a 1:1 ratio to a BIS of target 50 ('light' anaesthesia) or a BIS of target 35 ('deep' anaesthesia), with randomisation stratified by country.

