4.2 Sample size calculation

Chan *et al.* showed that delirium incidence was reduced from 24.1% to 15.6% with the use of BIS-guided anaesthesia versus routine care in a broadly similar patient group to the BALANCED Study cohort, with the exception that 83% were ASA 1 or 2. Using the data from Chan *et al.* we hypothesise that the incidence of delirium will be reduced from 25% in the deep anaesthesia group (BIS target 35) to 15% in the light anaesthesia group (BIS target 50). A power analysis using this reduction from 25% to 15%, with power of 80% and two-tailed alpha = 0.05, indicates that approximately 270 patients are required in each group (total of 540 patients). We therefore plan to recruit approximately n=600 patients to allow for all-cause loss-to follow-up.

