4.3.2 Per-protocol population

The per-protocol (PP) population is defined as all randomised participants in the sub-study who meet all the inclusion/exclusion criteria for BALANCED with BIS group classified according to the actual median BIS value achieved irrespective of randomisation. Participants will be allocated to the BIS=50 group if the achieved median BIS is between 45 and 55 inclusive, and to the BIS=35 group if the achieved median BIS is between 30 and 40 inclusive. Participants who are not within these ranges will be excluded from these analyses. The primary and secondary endpoints will be compared between the two groups defined as per-protocol.

5 *DEMOGRAPHIC AND BASELINE CHARACTERISTICS*

Participant demographic and baseline clinical characteristics will be summarised descriptively by randomised group. Summaries will include frequencies and percentages for categorical data and means, medians, ranges, standard deviations and inter-quartile ranges as appropriate for continuous data. These baseline summaries will include the following variables:

- Age
- Weight
- Sex
- Ethnicity
- ASA physical status

- Charlson score
- WHODAS score
- Cancer diagnosis
- Emergency/elective surgery
- Surgery type
- Haemoglobin
- Albumin
- Creatinine
- Surgical duration
- Pre-operative MMSE

These data will be examined for any imbalances between randomised treatments. No formal hypothesis testing will be conducted on these baseline variables.

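### The primary delirium test is valid and meets its power target, but it leaves age and pre-operative MMSE unused; pre-specified adjustment would probably add power without adding patients

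*Combined protocol and SAP*

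**What the plan says.** Section 7.1 tests the primary endpoint "using a Mantel-Haenszel Chi-square test, stratified by study-centre groups" and summarises the comparison by a pooled odds ratio with a 95% CI. No patient characteristic enters this test, and no adjusted sensitivity analysis of the primary endpoint is planned.

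Section 4.1 allocates patients 1:1 "with randomisation stratified by country". Section 4.3 places the 8 sites in Australia, Hong Kong, USA and China. The centre groups of section 7.1 are not defined anywhere. In section 7.2 the factor is called 'study-centre' in some models and 'centre-stratum' in another.

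Section 5 lists age and "Pre-operative MMSE" among the baseline variables. They are to be summarised by group and inspected for imbalance, but no analysis follows from that inspection. Demographic and other patient factors are related to delirium only in section 7.3, through exploratory stepwise models screened at p < 0.15.

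Section 4.2 states the hypothesis on the absolute scale: "we hypothesise that the incidence of delirium will be reduced from 25% in the deep anaesthesia group" to 15% in the light group. Section 8 rules out imputation of missing data.

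**The concern.** The trial has one confirmatory comparison, and section 7.1 adjusts it only for centre. Age and baseline cognition are natural candidates as predictors of delirium. The sponsor treats demographic factors as possible predictors in its own exploratory objectives (section 3.4). Baseline cognition may also vary widely in the primary population, because section 4.3.1 excludes only patients with pre-operative delirium. Patients with a pre-operative MMSE below 26 are dropped only from the cognitive impairment analysis.

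With a binary outcome, conditioning on a strong baseline predictor raises the power of the treatment test. The data are already collected, so forgoing the adjustment gives up precision for no saving. Two smaller matters belong with it. The strata of the primary test are open to a later choice, and the planned summary measure is an odds ratio although the hypothesis is a difference in incidence.

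**Working it through.** **1. The plan's sample size.** Inputs from section 4.2: p1 = 0.25, p2 = 0.15, "with power of 80% and two-tailed alpha = 0.05". The mean rate is 0.20.

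n = [1.96·√(2·0.20·0.80) + 0.842·√(0.25·0.75 + 0.15·0.85)]² / 0.10² = (1.109 + 0.472)² / 0.01 ≈ 250 per group.

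With the continuity correction: n' = (250/4)·[1 + √(1 + 4/(250·0.10))]² = 62.5·(1 + 1.077)² ≈ 270 per group. The plan's figure is reproduced exactly.

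**2. Power before adjustment.** Uncorrected two-proportion test:
- 270 per group: z = (0.10·√270 − 1.109)/0.561 = 0.952, power 83.0%.
- 300 per group (the recruitment target of 600): z = (0.10·√300 − 1.109)/0.561 = 1.111, power 86.7%.

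**3. Gain from adjustment.** The documents do not say how well age and MMSE predict delirium, so the strength is assumed. Simulation model: logit P(delirium) = a(arm) + site effect + g·x. Here x is one standard normal score standing in for age and MMSE together, and the intercepts are solved so that marginal incidence stays at 25% and 15%. There were 8 sites of equal expected size, 2 per country; allocation was balanced 1:1 within country. The SD of the site log-odds was 0 or 0.5 (assumed). Each setting had 3,000 trials, with a Monte Carlo standard error of about 0.65 points per power figure. Both methods were applied to the same simulated trials. Results for N = 540, as site SD 0 / site SD 0.5:

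| g | AUC | Mantel-Haenszel by site | Logistic: site + score | Gain (points) |
|---|---|---|---|---|
| 0.4 | 0.61 / 0.61 | 83.3% / 84.9% | 84.6% / 85.5% | 1.3 / 0.6 |
| 0.7 | 0.68 / 0.68 | 82.0% / 83.9% | 84.7% / 86.2% | 2.7 / 2.3 |
| 1.0 | 0.74 / 0.74 | 82.9% / 85.3% | 87.7% / 89.4% | 4.8 / 4.1 |
| 1.4 | 0.81 / 0.80 | 84.4% / 82.9% | 91.6% / 90.9% | 7.2 / 8.0 |

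At N = 600 the site-stratified test has 86.5% to 89.0% power and the adjusted model 87.5% to 94.5%, with gains of 0.8 to 6.4 points. In the one null setting run (N = 540), type I error was 4.8% for the site-stratified test and 4.9% for the adjusted model.

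A separate Wald calculation at 270 per group, without sites, agrees: about 82% unadjusted, 83% at AUC 0.61, 85% at 0.70 and 88% at 0.78.

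The plan does not say whether its Mantel-Haenszel statistic is continuity-corrected. With the correction, the site-stratified test had 79.5% to 82.2% power at N = 540. That difference comes from the correction and is not counted as a gain from covariates.

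**4. Country against centre.** In the same simulations at N = 540, Mantel-Haenszel by country had 82.4% to 85.5% power and by site 82.0% to 85.3%. Setting by setting, the two differed by at most 0.6 points, which is within simulation error.

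**5. Effect measure.** At 25% and 15%:
- risk difference = 0.25 − 0.15 = 10 points
- risk ratio = 0.15/0.25 = 0.60
- odds ratio = (0.15/0.85)/(0.25/0.75) = 0.53

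With the same marginal rates held fixed, the odds ratio conditional on the score is about 0.50 at AUC 0.70, 0.48 at 0.745 and 0.46 at 0.78.

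**The case against.** The strongest reply is that nothing is broken. A centre-stratified Mantel-Haenszel test is a standard, valid analysis, and steps 1 and 2 show that it meets its power target on the plan's inputs. This stands. A reader might infer that the trial is underpowered or its primary test faulty, and the documents support neither.

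Second, the size of the benefit is assumed. At an AUC of about 0.61 it is close to nothing, and it exceeds 7 points only near 0.80. This also stands: no single figure can be drawn from the documents.

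Third, a reader might infer that leaving country out of the primary test wastes power or discards the randomisation strata. Sites lie within countries, so strata that are single centres, or groups of centres within a country, already condition on country. Only groups that cross countries would lose it, and the plan nowhere says that it will form them.

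Fourth, the odds ratio misleads only if it is read as a risk ratio, and section 7.1 does not prevent incidence being reported by arm. That is fair. But adjustment moves the odds ratio further from 1, and from the risk ratio of 0.60, so an adjusted analysis needs an absolute measure beside it.

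Finally, a model containing MMSE conflicts with section 8 if any baseline scores are missing. This is correct, and the amendment has to deal with it.

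**Conclusion.** The point holds as a low-cost improvement to the only confirmatory comparison. Pre-specified adjustment for age and pre-operative MMSE would raise power by roughly 1 to 8 points at 540 analysed patients. This assumes that together they predict delirium with an AUC between 0.61 and 0.80, that one linear score represents them, and that incidence is 25% and 15% as planned. The direction is secure if they are prognostic at all; the size is not known.

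The undefined centre grouping leaves a choice open in the primary test, but it has not been shown to cost power or validity. Reporting a risk difference lets the trial answer its hypothesis on the scale on which it was stated.

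**What to change.** Amend the SAP before database lock, by the route in section 9:

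- **Primary model.** Logistic regression on randomised group, one fixed centre factor, age and pre-operative MMSE, with the functional form of both covariates stated. Test the treatment coefficient, which is the test that the power figures above refer to.
- **Centre factor.** Define it once, under one name, for every stratified test and model. If small centres must be pooled, fix the rule in advance on total enrolment without reference to treatment or outcome, and never pool across countries.
- **Effect measures.** Report the standardised (g-computation) risk difference with 95% CI as the main measure, and the conditional odds ratio beside it, labelled as conditional.
- **Supportive analysis.** Keep the Mantel-Haenszel test with the same strata, and state whether it is continuity-corrected.
- **Missing baseline MMSE.** Add an exception to section 8 for this covariate only, for example the overall mean plus a missing-value indicator, applied without reference to treatment, so that no ITT patient is dropped. The rule for outcomes is unchanged.

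The model is affordable. At 540 patients the planned rates give 270·0.25 + 270·0.15 = 108 expected events. There would be at most 12 parameters: intercept, 7 centre terms, treatment, age, MMSE and the missing indicator. That is about 9 events per parameter.

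The cost is SAP wording and programming, with no new data. The two downsides are an odds ratio not directly comparable with a Mantel-Haenszel one (about 0.46 to 0.50 against 0.53 over AUC 0.78 to 0.70) and a limited exception to the no-imputation rule.

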7.2 Secondary endpoint analyses

The analysis of the secondary endpoint the incidence of POD at each assessment time will be undertaken as supporting analyses of the primary

endpoint. These analyses will compare POD between randomised groups at each post-operative assessment, in the intention-to-treat population, using a Mantel-Haenszel Chi-square test, stratified by study-centre groups. The pooled estimate of the odds ratio and 95% confidence interval from this analysis will be used to summarise the statistical comparison. Analyses will be undertaken on both the Intention-to-Treat population and the Per-Protocol populations.

The analysis of the secondary endpoint the severity of POD, in the intention-to-treat population, will be undertaken using a general linear model with study-centre and randomized groups as fixed factors in the model. The mean difference between randomised groups derived from the model will be presented with the 95% confidence interval. If the distribution of the severity does not meet the assumptions for this parametric analysis then the severity maybe square root transformed prior to analysis. Analyses will be undertaken on both the Intention-to-Treat population and the Per-Protocol populations.

The analysis of the secondary endpoint the change in MMSE score at discharge, in the intention-to-treat population, will be undertaken using a general linear model with randomised group and study-centre as fixed factors in the analysis. The mean difference in the changes between randomised groups derived from the model will be presented with the 95% confidence interval. Analyses will be undertaken on both the Intention-to-Treat population and the Per-Protocol populations.

The analysis of the secondary endpoint the AMTS level at 3 and 12 months, in the intention-to-treat population, will be undertaken using a general linear model with randomised group and study-centre as fixed factors in the analysis. The mean difference in the levels between randomised groups derived from the model will be presented with the 95% confidence interval. Analyses will be undertaken on both the Intention-to-Treat population and the Per-Protocol populations.

The analysis of the secondary endpoint cognitive impairment at discharge (MMSE < 26) or at 3 and 12 months (AMTS<8) will be undertaken, in the intention-to-treat population, using a Mantel-Haenszel Chi-square test, stratified by study-centre groups. The pooled estimate of the odds ratio and 95% confidence interval from this analysis will be used to summarise the statistical comparison. Analyses will be undertaken on both the Intention-to-Treat population and the Per-Protocol populations, with all those identified as having cognitive impairment pre-operatively (MMSE < 26) excluded from the analyses.

The associations between POD incidence and subsequent MMSE changes at discharge and the AMTS levels at 3 and 12 months will be tested using a general linear model which will include randomised group, centre-stratum and

POD diagnosis as fixed factors and the MMSE change as the dependent variable.

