3.2 Primary Objective

To compare the post-operative incidence of delirium amongst patients undergoing major surgery between those randomised to a BIS of target 50 ('light' anaesthesia) compared with those randomised to a BIS of target 35 ('deep' anaesthesia).

Primary endpoint:

The incidence of post-operative delirium, defined as POD present at any of the 10 assessments over the 5 post-operative days. The 3

minute diagnostic interview for Confusion Assessment Method delirium (3D-CAM) or the CAM-ICU is used to determine the presence of delirium. This will be administered preoperatively and twice daily (05:00 -11:00 and 1800 – 2200) for 5 days postoperatively or until discharge. A modified version will be used for patients in ICU (CAM-ICU) who are unable to talk on these days. Delirium assessment will be performed when patients can be aroused sufficiently in order to be assessed for delirium (Richmond Agitation and Sedation Score >-4).

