3.3 Secondary Objectives

- To quantify and compare the temporal pattern of the incidence of POD amongst patients undergoing major surgery between those randomised to a BIS of target 50 ('light' anaesthesia) compared with those randomised to a BIS of target 35 ('deep' anaesthesia).
- To quantify and compare the severity of POD amongst patients undergoing major surgery between those randomised to a BIS of target 50 ('light' anaesthesia) compared with those randomised to a BIS of target 35 ('deep' anaesthesia).
- To quantify and compare the change in cognitive function at discharge (or 7 days) post-operatively between randomised groups.
- To quantify and compare the change in cognitive function at 3 and 12 months post-operatively between randomised groups.
- To quantify and compare cognitive impairment at discharge (or 7 days), 3 and 12 months post-operatively between randomised groups.
- To test the associations between POD incidence and subsequent MMSE changes or cognitive impairment and AMTS levels at discharge, or 3 and 12 months.

Secondary endpoints:

1. The incidence of postoperative delirium (POD) on each of the 5 post-operative days.
2. The number of postoperative delirium (POD) episodes over the 5 post-operative days (as a measure of delirium severity).
3. Cognitive change as measured by the Mini-Mental State Examination (MMSE) score at discharge (or 7 days).
4. Cognition level as assessed by modified MMSE (Abbreviated Mental Test Score - AMTS) administered at 3 and 12 months postoperatively by telephone.
5. Cognitive impairment defined as a score on the Mini-Mental State Examination (MMSE) at discharge (or 7 days) as <26 or as an AMTS

score of <8 at 3 and 12 months. Calculated for those with a score ≥ 26 pre-operatively.

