4.3.1 Intention-to-treat (ITT) population

All randomised participants participating in the sub-study who do not have a diagnosis of delirium pre-operatively will be included in the ITT population with treatment allocation based on randomised treatment. The primary and secondary endpoints will be analysed using the full analysis set population i.e. the intention-to-treat population which includes all randomised patients, without a pre-operative diagnosis of delirium undergoing induction of general anaesthesia for surgery.

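### The per-assessment delirium comparison measures point prevalence but is labelled incidence, so a difference in duration between arms could be read as a difference in new cases

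*Combined protocol and SAP*

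**What the plan says.** Section 3.3 sets a secondary objective: "To quantify and compare the temporal pattern of the incidence of POD amongst patients undergoing major surgery", light against deep. The matching endpoint 1 is "The incidence of postoperative delirium (POD) on each of the 5 post-operative days". Neither defines a new case or says who is at risk on a given day.

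Section 7.2 keeps the word incidence, stating that "the incidence of POD at each assessment time will be undertaken as supporting analyses of the primary" endpoint. It then gives the rule: "These analyses will compare POD between randomised groups at each post-operative assessment", by a centre-stratified Mantel-Haenszel test with a pooled odds ratio. The population is the intention-to-treat set of section 4.3.1, which "includes all randomised patients, without a pre-operative diagnosis of delirium undergoing induction of general anaesthesia for surgery". Pre-operative delirium is therefore the only delirium exclusion.

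The primary endpoint in section 3.2 is POD incidence "defined as POD present at any of the 10 assessments over the 5 post-operative days", so each patient counts once. Assessment is twice daily "for 5 days postoperatively or until discharge", and section 8 rules out imputation. Endpoint 2 is "The number of postoperative delirium (POD) episodes over the 5 post-operative days (as a measure of delirium severity"; an episode is not defined.

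**The concern.** The proportion of patients who are POD-positive at a given assessment depends on how many became delirious by then and on how many have not yet recovered. From the second assessment on, the planned comparison carries both. The primary endpoint carries only the first.

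Two things are at stake. The objective on the temporal pattern of incidence has no analysis that isolates new cases. And because section 7.2 presents these tests as supporting the primary endpoint, an arm difference on later days that comes only from longer episodes could be cited as evidence that anaesthetic depth changes the incidence of delirium.

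**Working it through.** **1. The plan's own figures.** The only delirium rates given for the two arms are 25% (deep) and 15% (light) in section 4.2, both cumulative. With 80% power and two-sided alpha 0.05, the two-proportion formula gives 250 per group without continuity correction and 270 with it, so the stated 270 (540 in total) reproduces. These figures say nothing about onset by day or about duration, so the size of the present problem can only be illustrated.

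**2. What is counted.** Endpoint 1 speaks of incidence on a day. The rule in section 7.2 compares POD status at an assessment. The population excludes only those delirious before surgery. No section removes a patient after a first positive result. A patient positive from day 1 to day 4 is therefore a case each time.

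**3. Illustration by day (all rates assumed).** Onset is identical in both arms: 8, 5, 3, 2.4 and 1.6% of patients on days 1 to 5. These sum to 20%, so the primary odds ratio is 1.0. Day-to-day persistence is 70% (deep) and 50% (light). Everyone is assessed, with no recurrence and no discharge.

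Prevalence on day i = sum over j ≤ i of onset(j) × persistence^(i−j). For day 3:
- Deep: 8 × 0.49 + 5 × 0.7 + 3 = 10.42%
- Light: 8 × 0.25 + 5 × 0.5 + 3 = 7.5%
- Odds ratio, light v deep: (0.075/0.925) / (0.1042/0.8958) = 0.70

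| Day | Deep % | Light % | OR | New cases among positives, deep / light |
|---|---|---|---|---|
| 1 | 8.0 | 8.0 | 1.00 | 100% / 100% |
| 2 | 10.6 | 9.0 | 0.83 | 47% / 56% |
| 3 | 10.4 | 7.5 | 0.70 | 29% / 40% |
| 4 | 9.7 | 6.2 | 0.61 | 25% / 39% |
| 5 | 8.4 | 4.7 | 0.54 | 19% / 34% |

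The cumulative first-onset proportion is 8, 13, 16, 18.4 and 20% in both arms.

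**4. Would it be detected?** z = difference / √[(p_D(1−p_D) + p_L(1−p_L))/n], unstratified. On day 5 with n = 300: 0.0371 / √[(0.0768 + 0.0446)/300] = 0.0371/0.0201 = 1.84, which gives power of about 45%. Days 3 and 4 give z of 1.25 and 1.61 (24% and 36%). With 270 per arm, power is 22, 33 and 42% on days 3, 4 and 5. At the expected values every 95% interval includes 1; for day 5 with 300 per arm it is 0.27 to 1.05.

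**5. Sensitivity, on the plan's ten-assessment scale.** Onset is again identical (20% in total), with mean duration 2 assessments in one arm and 3 or 4 in the other. The odds ratio (longer v shorter) is 1.00 at the first assessment. At the tenth it is 1.51 or 1.96 if onset is uniform, and 3.37 or 6.77 if onset is front-loaded (each assessment's share 0.6 of the one before). The high front-loaded ratios rest on very low prevalences: 0.4% v 1.4% or 2.7%. Moving the total from 15% to 25% hardly changes them. Among patients not yet delirious, the new-case rate is equal in both arms throughout.

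**The case against.** The strongest reply is that the plan uses incidence loosely to mean delirium being present. Section 3.2 defines the primary incidence that way, and on the same usage endpoint 1 and section 7.2 agree: both concern status. The primary endpoint is the union of the ten statuses, so showing the components beside it is reasonable. This stands as far as showing them goes. It does not justify calling them incidence or reading a later-day difference as support for an incidence effect, and it leaves the temporal-incidence objective without an analysis of new cases.

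It is also fair to say that the plan never states that prevalent cases are counted. That is inferred from the absence of any at-risk restriction. If another rule was meant, the SAP should state it.

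Three stronger readings are tempting and are not supported:
- *The stated objective is when delirium starts.* Section 3.3 speaks of the temporal pattern of incidence and does not mention onset.
- *The ten comparisons exactly decompose endpoint 2.* That would need an episode to mean a positive assessment and every patient to be assessed ten times. The first is undefined, and stopping assessment at discharge prevents the second for anyone discharged before day 5.
- *A false incidence difference will be reported.* This depends on duration actually differing between arms, and even with the assumed difference no single day passes 45% power.

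Finally, an analysis restricted each day to patients still in hospital with no earlier POD conditions on events after randomisation. From day 2 it no longer compares the randomised groups. That objection is accepted and shapes the fix.

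**Conclusion.** The point holds in a limited form. As written, a point prevalence is reported as incidence and offered in support of a cumulative-incidence primary endpoint. With equal onset and unequal duration, the labelled incidence odds ratio moves away from 1 as the days pass: 0.70, 0.61 and 0.54 on days 3 to 5 under one assumed set of rates, with the same direction under the other sets tried. The size rests wholly on assumed onset and duration, with complete assessment. In practice later denominators shrink to patients still in hospital, which could add to the effect or mask it.

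A reader might infer that the main result is in doubt. It is not: the primary endpoint, its test and the sample size are untouched. This is a correction that should be made to a secondary, supporting analysis.

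**What to change.** 1. In section 7.2, call the per-assessment comparisons point prevalence and do not present them as support for an incidence effect. State whether the unit is the day (endpoint 1, five) or the assessment (section 7.2, ten).
2. For the temporal-incidence objective, add an analysis of first POD: the cumulative proportion of each randomised group with POD found by the end of each of days 1 to 5, stratified by centre. Keep all intention-to-treat patients in the denominator, and state a rule for discharge and missed assessments. Under the same rule, the day-5 value is the primary endpoint.
3. Optionally, add a discrete-time first-onset model with day, centre and arm as supportive. Note that its day-specific estimates condition on no earlier POD and on still being in hospital.

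Cost: SAP wording and one extra analysis of assessments already planned; section 9 allows amendment before database lock. Downside: new cases are few on later days (about 9, 7 and 5 per arm on days 3 to 5 with 300 per arm under the assumed onset), so late-day estimates will be imprecise.

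### The MMSE-change and AMTS-level models leave out pre-operative MMSE as a covariate, which gives up precision, and the 3- and 12-month change objective has no matching baseline

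*Combined protocol and SAP*

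**What the plan says.** All references are to the combined protocol and SAP.

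- **MMSE at discharge (section 7.2).** The outcome is the change in score. The model is: "general linear model with randomised group and study-centre as fixed factors in the analysis. The mean difference in the changes between randomised groups". No baseline covariate is named.
- **AMTS at 3 and 12 months (section 7.2).** The model has the same two terms, and the reported quantity is "The mean difference in the levels between randomised groups derived from the model".
- **Populations (sections 4.3.2 and 7.2).** Both models are run in the intention-to-treat and the per-protocol populations. Per-protocol groups are formed from the achieved median BIS whatever the allocation, and patients outside the two BIS bands are dropped.
- **Baseline cognition (sections 5 and 6).** "Pre-operative MMSE" is on the list of baseline variables, and pre-operative MMSE assessments are counted in the participant flow. No pre-operative AMTS appears in either section or among the endpoints in section 3.3.
- **Objective (section 3.3).** One secondary objective is "To quantify and compare the change in cognitive function at 3 and 12 months post-operatively between randomised groups". The corresponding endpoint is a cognition level on the AMTS, taken by telephone after surgery.
- **Other use of baseline MMSE (sections 3.3 and 7.2).** It restricts the binary impairment analysis to patients scoring at least 26 before surgery.

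**The concern.** A change score uses the baseline with a fixed coefficient of one. If the true regression of discharge MMSE on pre-operative MMSE has a different slope, subtraction corrects too much or too little, and the residual variance is larger than it need be. The AMTS comparison does not use the baseline at all, although a measure of pre-operative cognition is available for the same patients. The plan already treats baseline cognition as relevant in its binary impairment analysis; the continuous analyses have no counterpart.

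What is at stake is the width of the confidence intervals for the continuous cognitive endpoints, and their exposure to whatever baseline difference happens to arise. The per-protocol comparison is more exposed, because its groups are not the randomised ones. Separately, one stated objective promises a change at 3 and 12 months that the described data cannot supply.

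**Working it through.** **Inputs from the documents.** Section 4.2 gives "power of 80% and two-tailed alpha = 0.05", an incidence "reduced from 25% in the deep anaesthesia group (BIS target 35) to 15% in the light anaesthesia group (BIS target 50"), and "approximately 270 patients are required in each group (total of 540 patients"). Allocation is 1:1 (section 4.1). Model terms are those in section 7.2.

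**Inputs not in the documents.** No SD, correlation, effect size or power is given for MMSE or AMTS. I write r for the correlation of the outcome with pre-operative MMSE, and s for the ratio of post-operative to pre-operative SD. Both are assumed over a range.

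**Step 1: the plan's own figure.** With mean proportion 0.20 and difference 0.10, the two-proportion formula gives n = [1.960 × √(2 × 0.20 × 0.80) + 0.8416 × √(0.25 × 0.75 + 0.15 × 0.85)]² / 0.10² = 250 per group. With the continuity correction, (250/4) × [1 + √(1 + 4/(250 × 0.10))]² = 270. The stated 270 is reproduced and is not in question. The plan to recruit about 600 implies a loss of 1 − 540/600 = 10%.

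**Step 2: variance of the treatment difference**, n per arm, common SD σ, large samples:

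- post-operative level only: 2σ²/n
- change score: 4σ²(1 − r)/n
- adjusted for baseline: 2σ²(1 − r²)/n

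So adjusted/change = (1 + r)/2, and adjusted/level-only = 1 − r². Entering baseline as a covariate in the change-score model gives the same treatment estimate as adjusting the discharge level, so the first ratio applies to MMSE and the second to AMTS.

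**Step 3: numbers.**

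| Model | r | Variance with covariate ÷ variance as planned | CI width × |
|---|---|---|---|
| MMSE change | 0.3 | 0.65 | 0.81 |
| MMSE change | 0.5 | 0.75 | 0.87 |
| MMSE change | 0.7 | 0.85 | 0.92 |
| AMTS level | 0.3 | 0.91 | 0.95 |
| AMTS level | 0.5 | 0.75 | 0.87 |
| AMTS level | 0.6 | 0.64 | 0.80 |

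For MMSE this is worth 1/0.85 − 1 = 18% to 1/0.65 − 1 = 54% more patients. In SD units at 270 per arm and 80% power, the detectable difference for the change score is 0.285, 0.241 and 0.187 at r = 0.3, 0.5 and 0.7. With the covariate it is 0.230, 0.209 and 0.172. Ignoring baseline gives 0.241 throughout, so below r = 0.5 with equal SDs the change score does worse than no baseline at all.

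**Step 4: unequal SDs (MMSE only).** In units of the baseline variance, the change score has s² + 1 − 2rs and the adjusted analysis has s²(1 − r²). Their difference is (rs − 1)², which is never negative, so there is no large-sample loss. The size of the gain does depend on s. At s = 0.8, r = 0.3 the ratio is 0.582/1.16 = 0.50. At s = 1.5, r = 0.7 it is 1.1475/1.15 = 0.998.

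**Step 5: chance imbalance.** Given an observed baseline difference D, the expected shift is (rs − 1)D in the change-score comparison. For AMTS it is the AMTS-on-MMSE slope times D, and that slope is unknown here. Under randomisation D averages zero. With equal SDs and r = 0.3 to 0.7 the MMSE shift is −0.7D to −0.3D. At s = 1.5, r = 0.7 it is +0.05D.

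**Step 6: objective against endpoint.** Section 3.3 states the objective as a change at 3 and 12 months. Its endpoint is a level, and section 7.2 analyses a level. MMSE and AMTS have different impairment cut-offs (below 26 and below 8), so one cannot be subtracted from the other. With no pre-operative AMTS described, a change cannot be formed.

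**The case against.** The planned intention-to-treat models are valid. Under 1:1 randomisation both a change-score comparison and a level comparison, with group and centre, estimate the treatment effect without bias from baseline on average. A reader might infer from the missing covariate that these results would be biased; the documents do not support that. A shift exists only conditional on an observed imbalance, and Step 5 shows that neither its size nor its sign can be fixed without r, s and the AMTS slope. This part of the objection stands in full.

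Pre-operative MMSE is also not ignored in the discharge analysis, since it is in the outcome by subtraction. Only the covariate term is missing. That stands too, and with unequal SDs the term may add almost nothing.

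It can be said that the change objective is merely loose wording: endpoint, analysis and the last secondary objective all speak of AMTS levels, so no analyst would be misled. That is fair as to consequences, but the objective still promises something that the described data do not provide.

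Finally, section 5 has baseline variables examined for imbalance, and section 7.3 plans multivariable models for MMSE change and AMTS. This helps little. Section 5 gives no rule for acting on an imbalance, so later adjustment would be post hoc, and section 7.3 does not name pre-operative MMSE as a candidate. Nor does randomisation protect the per-protocol comparison, where groups follow achieved BIS.

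**Conclusion.** The point holds as a matter of precision and consistency in the secondary endpoints. For AMTS, adding pre-operative MMSE leaves 64% to 91% of the planned variance if r is 0.3 to 0.6. For MMSE change it leaves 65% to 85% if r is 0.3 to 0.7 and the SDs are equal; over SD ratios of 0.8 to 1.5 this widens to 50% to 99.8%, so the gain may be close to nil. All these ranges rest on assumed correlations and large-sample formulas. In the per-protocol analysis baseline differences may be systematic, and the covariate would deal only with the part carried by pre-operative MMSE.

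It would be going too far to read this as an error that invalidates the cognitive analyses or must be corrected before they can be interpreted. The primary delirium analysis and the 270 per group are unaffected.

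**What to change.** 1. In section 7.2, add pre-operative MMSE as a covariate to the MMSE-change model and to the AMTS-level models at 3 and 12 months, in both populations.
2. In section 3.3, reword the 3- and 12-month change objective as a comparison of AMTS level adjusted for pre-operative MMSE.

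The cost is a few sentences and no new data, since pre-operative MMSE is already collected. There is one small downside. Patients without a pre-operative MMSE already have no change score, and no fill-in of the covariate can rescue that. They would now also drop out of the AMTS models. Section 8 rules out imputation, so keeping them would need an explicit amendment there allowing a missing-baseline rule for this covariate only. Otherwise the number dropped should be reported. The change should be made by SAP amendment before database lock, as section 9 provides.
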